Department of Anesthesiology
Professor and Director of Quality Improvement
Washington University School of Medicine
[name]
[name]
[name]
[contact]
[contact]

[name], MSN, BSN, CRNA
Assistant Director of the Certified Registered Nurse Anesthetist
(CRNA)
Washington University School of Medicine
Department of Anesthesiology
[name]
[name]
[name]

[name]
Associate Professor of Anesthesiology Washington University
School of Medicine
Department of Anesthesiology
[name]
[name]
[name]

[contact]
[contact]

WORLD HEALTH ORGANIZATION DATA SET

Primary Registry and Trial Identifying Number ClinicalTrials: NCT03923699

Date of Registration 23 April 2019

Secondary Identifying Numbers IRB ID#: 201903026

Source(s) of Monetary Support NINR R01NR017916, Institutional funds

Primary Sponsor Department of Anesthesiology - Washington University School of Medicine in St. Louis, MO

Role of Sponsors Sponsors did not contribute to any intellectual study design, collection, management, analysis or interpretation of the data and have no authority over these activities

Contact for Public Queries [name], MBBCh
Study Principal Investigator
[contact]
[contact]
[name]
Department of Anesthesiology [name]
Washington University School of Medicine
[name], United States

Contact for Scientific Queries [name], MBBCh
Study Principal Investigator
[contact]
[contact]
[name]
Department of Anesthesiology [name]
Washington University School of Medicine
[name], United States

Public Title: Protocol for the Telemedicine Control Tower for the OR: Navigating Information, Care and Safety (TECTONICS)

Scientific Title:	Effectiveness of an anesthesiology control tower system in improving perioperative quality metrics and clinical outcomes: a randomized, pragmatic trial
Countries of Recruitment	United States
Health Condition(s) or Problem(s) Studied	Determine the Anesthesiology Control Tower (ACT) system's effectiveness at preventing adverse outcomes and improving perioperative care quality care metrics.
Description of Intervention:	All 58 main operating rooms will be monitored by the ACT team. Operating rooms will be randomized daily to standard of care or intervention by the ACT team to assist the anesthesia clinicians with clinical decision making.
Key Inclusion and Exclusion Criteria	All patients 18 years or older undergoing surgery at Barnes Jewish Hospital in St. Louis, MO
Study Type	Interventional Allocation: Randomized Intervention model: parallel assignment Blinding: Anesthesia practitioner un-blinded to intervention, subject blinded to intervention, data analyst blinded to intervention, ACT Clinicians un-blinded to intervention Primary purpose: prevention Phase III
Date of First Enrollment	1 July 2019
Target Sample Size	40,000
Recruitment Status	Enrollment
Primary Outcome(s)	30-day mortality, postoperative delirium, postoperative respiratory failure, and postoperative acute kidney injury.
Key Secondary Outcomes	Perioperative quality of care metrics, including temperature management, antibiotic redosing, mean arterial pressure management, mean airway pressure with mechanical ventilation, blood glucose management, measured anesthetic concentration, and fresh gas flow rate.

ORGANIZATIONAL STRUCTURE AND RESPONSIBILITIES

Principal Investigator:

[name], MBBCh

Responsibilities include: design and conduct of the TECTONICS trial, preparation of protocol and revisions, organizing steering committee meetings, and publication of study reports.

Steering Committee:

[name], MBBCh	[name]	[name]
[name] [name]	[name]	[name]
[name]	[name]	[name]
[name]	[name], CRNA, CCRN	[name], MSN, BSN, CRNA
[name]	[name]	[name]

Responsibilities include: agreement of final protocol, reviewing progress of study and if necessary, changes to the protocol, coordinating with principle investigator, and communicating with trial management committee.

Operations Committee:

[name], MBBCh	[name]	[name]
[name]	[name]	[name]
[name]	[name], CRNA, CCRN	[name], MSN, BSN, CRNA
[name]	[name]	[name]
[name]	[name]	

Responsibilities include: study planning, organization of steering committee meetings, provides annual risk report to the Human Research Protection Office at Washington University, provides reports to Safety Monitoring Committee (SMC), reports serious adverse events to Washington University IRB (Institutional Review Board), ethics committee applications, data verification

Data Management Committee:

[name] [name]
[name]
[name]
[name]
[name]

Responsibilities include: statistical design of study, data verification, and statistical analysis.

Data Adjudication Committee:

[name], MBBCh	[name]	[name]
[name] [name]	[name]	[name]
[name]	[name],	[name], MSN, BSN,

Postoperative delirium	Defined as an acute change in consciousness or cognition. It has a fluctuating course, and is characterized by inattention, disorganized thinking and altered level of consciousness. We have trained the nursing staff on our surgical intensive care units to assess all patients for postoperative delirium using the Confusion Assessment Method for the Intensive Care Unit (CAM-ICU) instrument. ⁶⁴ It is administered every 12-24 hours depending on clinical context while in the ICU. All delirium assessments within 7 days will be included.
Postoperative respiratory failure	Defined as mechanical ventilation for greater than 24 hours after surgery, or unplanned postoperative re-intubation and mechanical ventilation within 48 hours of surgery. ⁶⁵ Planned staged operations are excluded.
Postoperative acute kidney injury	Diagnosed when any of the following three criteria are met: (i) an increase in serum creatinine by 50% compared with preoperative within 7 days, (ii) any increase in serum creatinine > 0.3 mg/dL in 48 hours, or (iii) oliguria (urine output < 0.5 mL/kg/hr for 6-12 hours). ^{33,66,67}

Table 2. Secondary outcome measures and definitions.

Measurement	Definition
Temperature management	Temperature $\geq 36^{\circ}\text{C}$ at end of surgery
Antibiotic redosing	Antibiotic redosing compliant with guidelines developed by the institutional pharmacy and therapeutics committee.
Mean arterial pressure management	Percentage time during surgery with mean arterial pressure ≥ 60 mmHg
Mean airway pressure with mechanical ventilation	Percentage time during surgery with mean airway pressure ≤ 30 cmH ₂ O.
Blood glucose management	Proportion of patients with blood glucose ≤ 200 mg/dL at end of surgery.
Measured anesthetic concentration	Proportion of patients without ≥ 15 consecutive min of anesthetic concentration ≤ 0.3 MAC during anesthetic maintenance period.
Fresh gas flow rates	Proportion of patients with efficient fresh gas flow for $\geq 90\%$ of the anesthetic maintenance period

Table 3. Primary outcomes to be assessed with estimation of power for each metric.

Primary adverse outcomes	Estimated current incidence	Target with ACT support	Power based on 40,000 patients in RCT ($p<0.005$)
Thirty-day postoperative mortality	2% ²⁻⁵	1.5%	84% (>80%)*
Postoperative delirium (only patients admitted to intensive care units [ICUs])	25% ^{68,69}	21%	93% (>80%)* (Based on 8,000 patients admitted to ICU)
Postoperative respiratory failure	2% ⁷⁰	1.5%	84% (>80%)*

Postoperative acute kidney injury	2% ^{71,72}	1.5%	84% (>80%)*
-----------------------------------	---------------------	------	-------------

*The adjusted power was calculated assuming a cluster-randomized design allowing for an intracluster correlation between 0.005 and 0.01 and varying number of patients per OR. The current incidence estimates on which these power analyses are based are consistent with findings in our previous studies^{4,5,12,51,55,56,58,68,69} as well as from the ACTFAST₂ pilot study, where we have approximations of these complications from ~110,000 (mostly inpatient) surgical patients at our institution over 5 years.

Table 4. Secondary outcomes to be assessed with estimation of power for each metric.

Secondary outcome measures	Estimated current compliance	Target with ACT support	Power based on 40,000 patients in RCT (p<0.005)
Temperature $\geq 36^{\circ}\text{C}$ at end of surgery	60%	70%	>99% (>90%)*
Antibiotic redosing adherence $\geq 90\%$	70%	90%	>99% (>90%)*
Percentage time during surgery with mean arterial pressure $\geq 60 \text{ mmHg}$	80%	85%	>99% (>90%)*
Percentage time with peak airway pressure $\leq 30 \text{ cmH}_2\text{O}$	75%	85%	>99% (>90%)*
Proportion with blood glucose $\leq 200 \text{ mg/dL}$ at end of surgery	75%	85%	>99% (>90%)*
Proportion without ≥ 15 consecutive min of anesthetic concentration $\leq 0.3 \text{ MAC}$ during maintenance period	95%	99%	>99% (>90%)*
Proportion with efficient fresh gas flow for $\geq 90\%$ of anesthetic period	75%	90%	>99% (>90%)*

*The adjusted power was calculated assuming a cluster-randomized design allowing for an intracluster correlation between 0.01 and 0.03 and varying number of patients per OR for a total N=40,000.

### Trial registration

<https://clinicaltrials.gov/ct2/show/NCT03923699>

### SAP and Protocol Versions

Protocol	SAP	Date
1.0	--	
1.0	1.0	2023 June 21
1.0	1.1	2023 Dec 13

### SAP Revisions.

1.0: first version

1.1: revisions based on review of available data

- Removed mean airway pressure outcome because it was not captured in the EHR. Replaced with peak airway pressure.
- Updated secondary outcomes to use the same method for multiplicity adjustment as the primary outcomes. There were not enough secondary outcomes for false-discover-rate type methods to be applicable.
- minor clarification in introduction
- operationalized detection of ACT not staffed (coordinator logs not available)
- added exclusion of subsequent cases during the outcome period of an index case to the population definition (previously in the analysis section)
- removed [[name] 2019] method for baseline risk as not all patients had preoperative assessments for included covariates. Replaced with model using only procedure text.
- removed driving pressure requirement defining duration of ventilation due to use of negative pressure (spontaneous) ventilation.
- switched from HC3 to HC1 standard errors due to the small cluster size, large number of clusters, and high computational load when bootstrapping.

## Section 2: Introduction

### Background and rationale

Telemedicine is a highly scalable approach to potentially increasing quality of health care. So far, the usefulness of telemedicine for intraoperative anesthesia clinicians has not been prospectively evaluated. The TECTONICS trial randomized a large number of patients to standard of care or telemedicine support from the Anesthesia Control Tower (ACT) including a modern system of real-time alerts for intraoperative problems and machine-learning based identification of high-risk patients.

### Objectives and hypotheses.

TECTONICS will rigorously assess the impact of a telemedicine intervention on patient-oriented outcomes: (1) death within 30 days (2) acute kidney injury (3) respiratory failure (4) postoperative delirium. We hypothesize that the incidence of each of these outcomes will be lower in the intervention group.

Secondary objectives include the effect of telemedicine support on quality of care metrics including (1) intraoperative normothermia (2) intraoperative normotension (3) lung-protective ventilation in the form of lower peak airway pressures (4) avoidance of postoperative hyperglycemia (5) avoidance of inadequate volatile anesthetic administration for age (6) appropriate antibiotic redosing (7) and avoidance of excessive volatile anesthetic consumption (high fresh gas flow).

We hypothesize that all the measures will have higher success rates in the intervention group.

## Section 3: Study Methods

TECTONICS is a parallel-group unblinded two-arm randomized superiority trial. The unit of allocation is operating room (OR)-days, with patients nested within OR-days. Randomization is 1:1 without any stratification based on patient factors to telemedicine support (intervention) or usual care (control).

### Randomization.

Pseudo-random number generation was performed centrally without stratification. Each day, a new row in a Microsoft SQL Server v17 database was created for each eligible OR included in the study. MS-SQL server's NEWID function was applied, and the rooms sorted by the resulting value, with the top

half (rounding down) of rooms allocated to control. Randomization therefore occurred with variable block size (due to occasional OR closures) centered on 58 or 59. Randomization occurred before any patient is eligible for intervention (before surgeries start). Randomization was periodically checked to be uncorrelated to room number. Randomization assignments were retrieved from the server automatically and displayed in the ACT.

#### Sample size.

The protocol document contains the assumptions used during trial design. Approximately 40,000 total patients were initially planned, acknowledging that changes at the study site suggested that accrual could proceed more quickly than prior data would suggest. Mid-way through the study, accrual was occurring at nearly double the estimated rate. The study PI and DSMB agreed to increase the target to 80,000 total patients to improve the likelihood of detecting small but clinically relevant differences in the primary outcome and to increase power in subgroups.

#### Framework

Superiority testing for all comparisons.

#### Statistical interim analyses and stopping guidance.

No interim efficacy analyses were planned. DSMB reports included group outcome rates, but no harm evaluation triggers were specified. No modifications to the analysis were planned.

#### Timing of final analysis.

The final analysis will be performed after a database lock with all patient data available.

#### Timing of outcome assessments.

Outcomes are assessed in a 30-day window after randomization.

### Section 4: Statistical Principles

#### Confidence intervals and p-values.

Level of significance. p-values (and interval alpha values) less than .005 will be reported as convincing evidence. Values between .005 and .05 will be reported as suggestive evidence.

#### Multiplicity Adjustment

Primary outcomes will be reported with family-wise error rate control using the permutation-based methods of (Romano 2016). Secondary outcomes will be reported with adjustment to control the family-wise error rate using the same method and separate alpha budget.

#### Confidence intervals to be reported.

Wald-type 95% and 99.5% confidence intervals will be reported for the primary outcomes. We will report Bonferroni-adjusted and unadjusted confidence intervals.

#### Adherence and protocol deviations

Because the protocol allows telemedicine clinicians to contact intervention ORs at their discretion (many rooms have no indication for contact), and there are many more operating rooms than could feasibly be contacted, a useful per-protocol analysis is not possible. We will report the rate and type of contacts from the telemedicine clinicians to operating rooms by randomization status.

The protocol specifically allowed for contact between the ACT and control rooms where necessary to prevent imminent patient harm.

We will present the rate and rationale for cross-over from control to intervention.

### Study Populations

Full Analysis Set: All adult patients with surgery in an eligible OR whose case is started during or within the 45 minutes before the ACT opens are included in the intention to treat population. The original protocol did not include the 45 minute grace period, which was added in discussion with the DSMB to include a larger number of cardiac cases which start earlier than general ORs at the study site. DSMB analysis initially included all patients whose surgery started *and* ended within the hours of the ACT. Patients with scheduled surgery who do not proceed to the OR are not included. Surgeries during days in which the ACT is not staffed are not included. Inclusion does not depend on outcome assessment; imputation of missing outcomes is discussed below. No other populations will be reported.

## Section 5: Trial Population

### Screening.

Surgeries are automatically checked against a list of approved operating rooms. Ages are automatically extracted from the electronic health record to verify adult status. Patients with unknown ages (for example, victims of violence with redacted personal information) are included.

### Eligibility criteria:

All adults (18 years and older) undergoing surgical procedures with anesthesia services in these operating rooms are included. Labor and operative delivery is conducted in a separate administrative area and is also excluded unless it occurs in the main surgical ORs. There are no other exclusion criteria related to procedure type, comorbid illnesses, or planned disposition other than the requirement that some anesthesia clinician be requested (excluding e.g. organ procurement and minor procedures performed without anesthesiology services) and the requirement for the procedure to take place in an operating room (excluding sedation-based procedure suites such as the cardiac diagnostic laboratory).

Subsequent surgeries on an included patient are not eligible until the 30-day outcome window of the index case has been concluded.

### ACT Staffing exclusion

Because study coordinators did not track days in which the ACT was closed due to a lack of medical staff, we infer it using the activity log in the AlertWatch interface. Days in which no activity is recorded after 10am are excluded.

### Recruitment

Recruitment is automatic with a waiver of consent.

### Withdrawal and follow up.

Because the trial accrues with a waiver of consent, withdrawal is not possible. Outcome imputation is discussed in the analysis section below.

### Baseline characteristics

Baseline measured characteristics and their summaries will include:

Name	Type	Summary	Distance Measure
Age	Continuous	Mean, SD	SMD

Race	Categorical	Proportions	Phi
Ethnicity	Binary	Proportion	Cohen's d
ASA-PS	Categorical	Proportions	Phi
Atrial fibrillation	Binary	Proportion	Cohen's d
Anemia	Binary	Proportion	Cohen's d
Asthma	Binary	Proportion	Cohen's d
Coronary Artery Disease	Binary	Proportion	Cohen's d
Current Cancer	Binary	Proportion	Cohen's d
Chronic Kidney Disease	Binary	Proportion	Cohen's d
ESRD	Binary	Proportion	Cohen's d
COPD	Binary	Proportion	Cohen's d
Stroke or TIA	Binary	Proportion	Cohen's d
Dementia or MCI	Binary	Proportion	Cohen's d
Diabetes	Binary	Proportion	Cohen's d
DVT or PE	Binary	Proportion	Cohen's d
Obstructive Sleep Apnea	Binary	Proportion	Cohen's d
Hypertension	Binary	Proportion	Cohen's d
Anesthesia Type	Categorical	Proportions	Phi
Functional Capacity	Categorical	Proportions	Phi
Surgical service	Categorical	Proportions	Phi
Procedure-specific mortality	Continuous	Median, IQR	SMD

### Secondary outcome measures and definitions.

Measurement	Definition																																																			
Temperature management	Temperature $\geq 36^{\circ}\text{C}$ at end of surgery (maximum temperature in the final 10 minutes of intraoperative record).																																																			
Antibiotic redosing	Antibiotic redosing compliant with guidelines developed by the institutional pharmacy and therapeutics committee. Patients without an indicated redosing event are excluded.																																																			
	
  
 Antibiotic	Adult Dose	Redosing Interval	
   
 Ampicillin/sulbactam	3 g	q2h	
 
 Aztreonam	2 g	q4h	
 
 Cefazolin	< 120 kg: 2 g ≥ 120 kg: 3 g	q4h	
 
 Cefepime	2 g	q4h	
 
 Cefoxitin	2 g	q2h	
 
 Ceftriaxone	2 g	q12h	
 
 Ciprofloxacin	400 mg	q8h	
 
 Clindamycin	900 mg	q6h	
 
 Ertapenem	1 g	q24h	
 
 Gentamicin (traditional)	1.5 mg/kg	q8h	
 
 Gentamicin (extended interval)	5 mg/kg	q24h	
 
 Linezolid	600 mg	q10h	
 
 Meropenem	1000 mg	q2h	
 
 Metronidazole	500 mg	q8h	
 
 Piperacillin/tazobactam	3.375 g	q2h	
 
 Vancomycin	< 80 kg: 1 g ≥ 80 kg: 1.5 g	q12h	
  
	Antibiotic	Adult Dose	Redosing Interval 	Ampicillin/sulbactam	3 g	q2h	Aztreonam	2 g	q4h	Cefazolin	< 120 kg: 2 g ≥ 120 kg: 3 g	q4h	Cefepime	2 g	q4h	Cefoxitin	2 g	q2h	Ceftriaxone	2 g	q12h	Ciprofloxacin	400 mg	q8h	Clindamycin	900 mg	q6h	Ertapenem	1 g	q24h	Gentamicin (traditional)	1.5 mg/kg	q8h	Gentamicin (extended interval)	5 mg/kg	q24h	Linezolid	600 mg	q10h	Meropenem	1000 mg	q2h	Metronidazole	500 mg	q8h	Piperacillin/tazobactam	3.375 g	q2h	Vancomycin	< 80 kg: 1 g ≥ 80 kg: 1.5 g	q12h
Antibiotic	Adult Dose	Redosing Interval 																																																		
Ampicillin/sulbactam	3 g	q2h																																																		
Aztreonam	2 g	q4h																																																		
Cefazolin	< 120 kg: 2 g ≥ 120 kg: 3 g	q4h																																																		
Cefepime	2 g	q4h																																																		
Cefoxitin	2 g	q2h																																																		
Ceftriaxone	2 g	q12h																																																		
Ciprofloxacin	400 mg	q8h																																																		
Clindamycin	900 mg	q6h																																																		
Ertapenem	1 g	q24h																																																		
Gentamicin (traditional)	1.5 mg/kg	q8h																																																		
Gentamicin (extended interval)	5 mg/kg	q24h																																																		
Linezolid	600 mg	q10h																																																		
Meropenem	1000 mg	q2h																																																		
Metronidazole	500 mg	q8h																																																		
Piperacillin/tazobactam	3.375 g	q2h																																																		
Vancomycin	< 80 kg: 1 g ≥ 80 kg: 1.5 g	q12h																																																		
Mean arterial pressure management	Fraction of time during surgery with mean arterial pressure $\geq 60$ mmHg																																																			
Peak inspiratory pressure with mechanical ventilation	Fraction of time during surgery with peak inspiratory pressure $\leq 30$ cmH 2 O. Only cases with mechanical ventilation are included. Mechanical ventilation is detected with sustained EtCO 2 $> 20$ mmHg, tidal volume $> 150$ mL, PEEP $> 2$ cmH 2 O. The first and last 8 minutes are excluded to account for activities around intubation and extubation.																																																			
Hyperglycemia	Blood glucose $> 200$ mg/dL at end of surgery (first glucose measurement after anesthesia stop within 24 hours).																																																			

Anesthetic delivery	Patients without $\geq 15$ consecutive min of volatile anesthetic concentration $\leq 0.3$ MAC during mechanical ventilation, defined as in “Peak inspiratory pressure” above. Patients with doses of sedatives at greater than the following dose-rates are excluded: propofol $> 40$ mcg/kg/min, ketamine $> 0.3$ mg/kg/hr.
Fresh gas flow rates	Proportion of patients with efficient fresh gas flow for $\geq 90\%$ of the mechanical ventilation period defined above. “Efficient” fresh gas flow is defined as $\leq 2$ L/minute for sevoflurane and $\leq 1$ L/minute for isoflurane and desflurane. Only times with $> 0.3$ age adjusted MAC are included.

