In ORs randomized to intervention, ACT clinicians contact OR clinicians in two phases. First, the ACT messages the OR clinician an individualized risk assessment and considerations / recommendations based on the preoperative evaluation and real time information from the monitors in the OR. The recommendations are geared towards (1) preventing major complications (Table 1) based on patients' specific risk profiles (e.g. history of stroke, hypertension, type 1 diabetes, coronary artery disease, valvular heart disease, pulmonary disease) and (2) adhering to general quality of care indicators (Table 2). The recommendations are based on the best currently available evidence (e.g. intensive insulin management in type 1 diabetes). OR clinicians are encouraged to reply to the message with specific concerns they would like to discuss, risk assessments they believe to be erroneous, and additional monitoring that they would like the ACT to perform. The second phase occurs during procedures. The ACT monitors physiologic and process alerts generated by AlertWatch® and ML algorithms, filters these alerts for those believed relevant and actionable, and contacts the anesthesia team where deemed appropriate. OR clinicians receiving notification from the ACT may choose to carry out whatever course of action they deem clinically appropriate. Anesthesia clinicians in the OR have access to the institution's "clinical" AlertWatch software, but do not have access to the "research" view.

Usual care

In ORs randomized to usual care, the ACT monitors patients, but the ACT clinicians does not contact the OR clinicians unless the ACT clinicians believe it to be clinically necessary for patient safety purposes (e.g. neuromuscular blockade without evidence of hypnotic agent administered). Concomitant care is provided in the usual perioperative setting with no modifications based on the trial. Anesthesia clinicians in the OR have

access to the institution's "clinical" AlertWatch software, but do not have access to the "research" view.

Risk forecasting algorithms

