We anticipate a possible contamination (or learning) effect over time in the usual care group. Clinicians are included in both intervention and control ORs (possibly on the same day) and may become sensitized to the standards of practice and the surrogate outcome measures being tracked, leading to “overlapping” improvements in these measures (as well as clinical outcomes) in both groups over the course of the study. This learning effect might manifest most strongly among clinicians who spend time in the ACT. Furthermore, with the knowledge that clinical behaviors are being observed, there is a high likelihood of a Hawthorne effect.^{45,46} In the reverse of the usual Hawthorne problem, the effect of being observed *in the intervention arm* represents part of the actual effect of the intervention; knowing that they are being observed, clinicians may feel more accountable to following perioperative best practices, and this is a meaningful effect. However, the non-contact rooms are also aware of the trial and enjoy the same improvement, falsely decreasing the estimated effect size. The data we have obtained prior to instituting the ACT will be useful in assessing the extent of contamination. Specifically, we will assess the intensity/frequency of contamination by comparing the outcomes of the control group patients to those of matched patients who had similar surgeries, demographics, and health conditions during the immediate period prior to the ACT implementation. We will also analyze control arm results in 3-month time bins (with baseline data for reference) to evaluate secular trends which may represent contamination, as well as the magnitude of clustering design effects.

Analysis of primary and secondary outcomes

Comparisons between groups during the randomized study will be with parametric and non-parametric statistical tests, according to the distributions of the measures of interest. Fisher’s exact or χ^2 test will be used to assess differences between proportions (the majority of assessments). Contingency statistical tests will be used to compare

occurrence of hypotension, hyperglycemia, hypoglycemia, and hypothermia between groups; and unpaired t-test or Mann-Whitney U-test, as appropriate, will be used to compare the durations of these occurrences between groups. All comparisons will use the intention-to-treat principle.

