### Harms

Harms will be analyzed using qualitative methods (thematic analysis) of case-report forms.

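### The protocol says hypoglycemia will be compared between arms; the SAP neither specifies nor withdraws that comparison, so a rise in low glucose would appear in no planned between-arm result

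*SAP*

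**What the plan says.** **Protocol, Analysis of primary and secondary outcomes.** Contingency tests are to compare the "occurrence of hypotension, hyperglycemia, hypoglycemia, and hypothermia between groups". An unpaired t-test or Mann-Whitney test is then to "compare the durations of these occurrences between groups".

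**Protocol, Tables 2 and 4.** The glucose metric is the "Proportion of patients with blood glucose ≤ 200 mg/dL at end of surgery". It has no lower bound. Table 4 gives 75% current compliance, a target of 85%, and power above 99% (above 90% allowing for clustering) with 40,000 patients at p<0.005.

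**Protocol, Intervention group.** One example of the advice the control tower may send is "intensive insulin management in type 1 diabetes".

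**SAP, Objectives and hypotheses.** The glucose objective is "avoidance of postoperative hyperglycemia".

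**SAP, Secondary outcome measures and definitions.** The outcome is named hyperglycemia. It is a value above 200 mg/dL "at end of surgery (first glucose measurement after anesthesia stop within 24 hours").

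**SAP, Harms.** "Harms will be analyzed using qualitative methods (thematic analysis) of case-report forms".

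**The concern.** The protocol sentence names four conditions. Three have a quantitative counterpart in the SAP and the fourth, hypoglycemia, has none. The SAP gives no reason, so a reader cannot tell a decision from an oversight.

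Two things are at stake. The first is safety reporting. Patients are enrolled under a waiver of consent that rests on minimal risk, and the protocol itself cites insulin advice as an example of the intervention's content. A between-arm count of low glucose is what a reader would look for beside the glucose result. The second is interpretation. A lower rate of values above 200 mg/dL means one thing if low values are unchanged and another if they rose. The planned output cannot separate the two.

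**Working it through.** **1. The four conditions side by side**

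| Named in the protocol sentence | Counterpart in the SAP |
|---|---|
| Hypotension | Fraction of surgery time with mean arterial pressure at or above 60 mmHg; time-weighted pressure below 65 mmHg as a sensitivity analysis |
| Hypothermia | Temperature at or above 36 °C at end of surgery; average temperature as a sensitivity analysis |
| Hyperglycemia | Glucose above 200 mg/dL, one reading |
| Hypoglycemia | None in the objectives, outcome definitions, sensitivity analyses, subgroups or harms |

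The one planned glucose subgroup, which removes patients without diabetes, reuses the above-200 definition. Where the SAP departs from the protocol elsewhere, it says so in the text: the 45-minute grace period (Study Populations) and the index-case rule (Analysis Methods). No such statement covers hypoglycemia.

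**2. What the planned metric can and cannot show**

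Among patients with a qualifying reading, let E be the proportion above 200 mg/dL, L the proportion below whatever low threshold is chosen, and 1 − E − L the rest. The SAP compares only E between arms.

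- A patient moved from the middle range to a low value leaves E unchanged.
- A patient moved from above 200 to a low value lowers E exactly as much as one moved into the middle range.

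At the Table 4 figures, E is 25% in control and 15% in intervention. The 10-point result is the same for any value of L within the remaining 75% and 85%. A single first reading after anesthesia stop also misses an intraoperative low already corrected, and it cannot yield a duration.

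**3. The plan's own power figure**

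Inputs from Table 4: p1 = 0.75, p2 = 0.85, 40,000 patients. With 1:1 allocation, n = 20,000 per arm. Alpha is 0.005, taken as two-sided.

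Power = Φ{[|p1 − p2|·√n − z·√(2·p̄·(1 − p̄))] / √(p1(1 − p1) + p2(1 − p2))}, with z = z(0.9975) = 2.807 and p̄ = 0.80.

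- Numerator: 0.10 × 141.42 − 2.807 × √0.32 = 14.142 − 1.588 = 12.554.
- Denominator: √(0.1875 + 0.1275) = 0.5612.
- Ratio 22.4, so power exceeds 99.9%.

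For clustering, n is divided by 1 + (m − 1)·ICC. Table 4 gives an ICC of 0.01 to 0.03. Mean cluster size m is not given, so 2 to 20 is assumed. The worst case is 1 + 19 × 0.03 = 1.57, and power still exceeds 99.9%. The stated figures reproduce. About 533 evaluable patients per arm would give 90% power: [(1.588 + 1.282 × 0.5612)/0.10]² ≈ 533.

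**4. What a hypoglycemia comparison could detect (assumptions only)**

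The documents give no hypoglycemia rate, threshold or fraction measured. The table uses the same formula with the SAP's target of 80,000 patients, two-sided alpha 0.005 and no clustering or multiplicity adjustment. It shows power for assumed control rates.

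| Fraction measured (assumed) | Rate ratio | 0.5% | 1% | 2% |
|---|---|---|---|---|
| 100% (40,000 per arm) | 1.5 | 95% | >99% | >99% |
| 50% (20,000 per arm) | 1.5 | 64% | 96% | >99% |
| 25% (10,000 per arm) | 1.5 | 29% | 65% | 96% |
| 25% (10,000 per arm) | 2.0 | 90% | >99% | >99% |

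The comparison would be informative over much of this range. Where few patients are measured and events are rare, a non-significant result would not exclude a 1.5-fold rise, so an interval is needed as well as a p-value.

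**The case against.** The best defense is that hypoglycemia was never a listed outcome. The protocol sentence sits in a paragraph about choice of test, gives no definition or threshold, and is not matched by any row in Table 2 or Table 4. That stands: no endpoint has been removed. But the sentence says what will be compared between groups, and the SAP leaves it unanswered.

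A second defense is that safety is monitored. The Safety Monitoring Committee reviews all adverse events and looks at study data every six months, and the monitoring board's reports included outcome rates by group. This is relevant, but hypoglycemia is not among the outcomes defined in the SAP, no harm triggers were set, and neither route gives a pre-specified between-arm result.

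A reader might also infer stronger points that the documents do not support:

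- *The SAP credits hypoglycemia as benefit.* A low reading is a non-event in either arm. It helps the intervention only if that patient would otherwise have exceeded 200 mg/dL. The accurate statement is that low glucose is not measured.
- *The SAP made the metric one-sided.* Protocol Tables 2 and 4 already had no lower bound.
- *The SAP revision list conceals the change.* That list covers SAP 1.0 to 1.1 only. Nothing shows that version 1.0 held a hypoglycemia analysis.
- *The intervention promotes intensive insulin generally.* It is one example, confined to type 1 diabetes, and operating-room clinicians stay free to act as they judge fit.

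**Conclusion.** The point holds as a protocol–SAP mismatch with a consequence for safety reporting. Followed as written, the analysis would yield one glucose result, in one direction and from one reading. A change in low glucose in either arm would appear in no quantitative comparison.

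The primary outcomes are untouched. The size of any hypoglycemia difference is unknown, and nothing in the documents shows that one exists. What can be stated is the imbalance: power above 99% to show the targeted 10-point gain, against no planned test of the opposite risk. The illustrative power figures rest wholly on assumed event rates and measurement fractions. The change is worth making because it is cheap and affects how the hyperglycemia result can be read.

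**What to change.** Reconcile the protocol's analysis section with the SAP's secondary outcome definitions by adding to SAP Section 6:

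- **Comparison.** The proportion of patients with hypoglycemia by arm, at a threshold the sponsor fixes before unblinding. Use glucose values from the health record, both intraoperative and within the 24-hour window already used for the hyperglycemia outcome.
- **Method.** The cluster-robust rate ratio in SAP Analysis Methods, with its confidence interval, overall and in the diabetes subset already planned.
- **Measurement.** By arm, the number of patients with any glucose value and the number of measurements per patient. If contact from the control tower prompts more checks, more lows will be found in that arm regardless of true incidence. The protocol recognizes this screening bias for kidney injury and delirium.
- **Interpretation.** A statement that the hyperglycemia result is read alongside this one.
- **Duration.** If duration cannot be derived from intermittent readings, declare its removal as a protocol deviation.

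The cost is one additional extract of glucose values and one table. The documents do not show that intraoperative and serial postoperative values have already been pulled, so the extract should be budgeted for. No patients or visits are added.
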